Inclusion Criteria	Exclusion Criteria

 • Age \geq 18 • Admitted to the ICU within 48h prior to enrollment • Likely to remain in the ICU (alive) for \geq72h • Naso/orogastric tube or ability to swallow • High risk of severe AKI* 	
 • Total serum calcium > 9.0 mg/dl or phosphate > 6.0 mg/dL within previous 48h • Currently receiving oral calcium supplementation • Ingestion of vitamin D₃ >1,000 IU/day or any 25D or 1,25D during the previous 7 days • AKI stage 2 or 3 (based on SCr and/or UOP criteria) • History of transplantation or chronically (>7days) receiving immunosuppressive medications (not including glucocorticoid steroids at a dose \leq prednisone 20 mg/day) • Neutropenia (<1000 PMNs/mm³) in the previous 48h • Primary parathyroid disease (active), granulomatous disease (active), or symptomatic nephrolithiasis in the previous 3 months • Receiving cytochrome P450 inhibitors[†] • CKD stage V or ESRD • Hgb < 7 g/dL • GI malabsorption • Prisoner • Pregnant or breastfeeding • Enrolled in a conflicting study, including any study with a research blood draw

Table 2. Inclusion and Exclusion Criteria. *Patients are considered to be at high risk of severe AKI if they have either: AKI stage 1, defined as an increase in SCr \geq 0.3 mg/d within the previous 48 hours, \geq 50% within the previous 7 days, or urine output \leq 0.5 ml/kg/h x 6 hours); or if they have an AKI risk score \geq 6 – see Table 3. [†]Patients will be excluded if they are receiving any of the following medications: ketoconazole, atazanavir, clarithromycin, indinavir, itraconazole, nefazodone, nelfinavir, ritonavir, saquinavir, telithromycin, or voriconazole, since these drugs may inhibit enzymes involved in vitamin D metabolism.

Risk Factor	Points
Chronic	
Age > 70y	1
Hypertension	1
Diabetes Mellitus	2
Chronic Liver Disease (cirrhosis, NAFLD, AIH, or chronic viral hepatitis)	2
Congestive Heart Failure (NYHA class 3 or 4)	2
Chronic Kidney Disease (baseline eGFR < 60 ml/min/1.73m ²)	3
Acute	
Blood pH (venous or arterial) \leq 7.30	2
Sepsis	2
Mechanical ventilation expected to last > 24 hours	2
Hypotension/shock, defined as MAP < 70 mm Hg or use of pressors/inotropes	2

Table 3. AKI Risk Prediction Score

B. Source of Subjects

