Participants will be randomly assigned, in a 1:1:1 fashion, to receive calcifediol, calcitriol, or placebo. Randomization will be stratified by the presence or absence of AKI on enrollment, defined by an increase in serum Cr ≥ 0.3 mg/dl within the previous 48 hours, $\geq 50\%$ within the previous 7 days, or urine output ≤ 0.5 ml/kg/h x 6 consecutive hours during any 6-hour block in the previous 24 hours. Randomization will be performed by the BWH research pharmacy using a computer generated sequence and permuted blocks.

V. STUDY PROCEDURES

A. Parameters to be measured

Clinical data

Upon enrollment in the study, the following demographic variables will be recorded: age, gender, race, ethnicity, comorbidities, active medications, active medical issues, reason for ICU admission, date of ICU/hospital admission, ICU location (e.g., MICU, CCU), and severity of illness at the time of study enrollment, as measured by APACHE II and SOFA scores.

In addition, the following clinical outcomes data will be recorded:

- ICU-, hospital-, and 28-day mortality
- ICU and hospital length of stay
- Incidence/severity of new/worsening AKI (defined by KDIGO guidelines)⁸⁸ within 1 week of enrollment
- Duration of mechanical ventilation
- Duration of vasopressor support
- Daily Sequential Organ Failure Assessment (SOFA) scores for the first 7 days of the study
- Physiologic data including heart rate, blood pressure, oxygenation, and urine output during the first 7 days of the study
- Hypocalcemia requiring I.V. calcium replacement during the first 7 days of the study
- Total serum calcium levels on a daily basis for the first 7 days of the study

28-day mortality

[figure not shown]
For patients discharged from the hospital prior to day 28, investigator [name]. will ascertain 28-day survival by calling the patient and/or their surrogate 28 days after enrollment as a courtesy follow-up to thank them for participating and to answer any questions they may have. The duration of the phone call is expected to last less than 2 minutes.

Blood samples

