All patients enrolled will have total serum calcium levels monitored on a daily basis as part of routine clinical care in the ICU. All subsequent doses of study drug will be held for any patient who develops a total serum calcium level > 10.0 mg/dl after enrollment. Additionally, if at any time during the course of the study >10% of participants in either of the active treatment arms develops hypercalcemia, defined as per the BWH hospital laboratory as a total serum calcium level > 10.7 mg/dl, the dosing regimen for future participants assigned to that arm will be reduced by 25%. For the calcifediol arm, this 25% dose reduction would result in a new dosing regimen of 300 µg on day 0 and 150 µg on days 1, 2, 3, and 4. For the calcitriol arm, this 25% dose reduction would result in a new dosing regimen of 3 µg daily for 5 days. Unblinded safety data on hypercalcemia will be evaluated by the data and safety monitoring board (DSMB).

G. Adaptive Trial Design

After enrollment of the first 18 patients (6 patients in each of the three arms), we will stop enrollment to measure plasma 25D levels in the patients who received calcifediol to ensure that mean plasma 25D levels on days 1, 2, 3, 4, and 5 are > 50 ng/ml. If mean plasma 25D levels on days 1, 2, 3, 4, and 5 are < 50 ng/ml and the mean increase in serum total calcium levels from day 0 to day 5 is < 0.5 mg/dl, we will increase the dosing regimen for the calcifediol arm for the remaining study participants as follows:

Mean plasma 25D level on days 1 through 5	Calcifediol dose adjustment for remaining participants
40-50 ng/ml	500 µg on day 0 and 250 µg on days 1, 2, 3, and 4
<40 ng/ml	600 µg on day 0 and 300 µg on days 1, 2, 3, and 4

VI. BIOSTATISTICAL ANALYSIS

A. Specific data variables being collected for the study

The specific data variables that will be collected are provided in section V-A.

B. Study end points

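### V.G's dose check averages in 25D samples taken after V.F has held dosing for high calcium, so a safety hold can read as under-dosing; the two sections need to be reconciled

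*Combined protocol and SAP*

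**What the plan says.** Section V.G (Adaptive Trial Design) sets one interim check of the calcifediol dose: "After enrollment of the first 18 patients (6 patients in each of the three arms), we will stop enrollment to measure plasma 25D levels". The set of patients whose samples count, and the aim of the check, are given as follows: "in the patients who received calcifediol to ensure that mean plasma 25D levels on days 1, 2, 3, 4, and 5 are > 50 ng/ml". Escalation needs two conditions together. The first is on exposure: "If mean plasma 25D levels on days 1, 2, 3, 4, and 5 are < 50 ng/ml". The second is on calcium: "the mean increase in serum total calcium levels from day 0 to day 5 is < 0.5 mg/dl". A table then gives one increase for a mean of 40 to 50 ng/ml and a larger one below 40.

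Section V.F (Dosing modifications) contains two other rules. One is individual: "All subsequent doses of study drug will be held for any patient who develops a total serum calcium level > 10.0 mg/dl after enrollment". The other acts on the arm: if ">10% of participants in either of the active treatment arms develops hypercalcemia", defined as calcium above 10.7 mg/dl, the regimen for future participants in that arm is cut by 25%.

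Two further items bear on the point. The exclusion criteria in Table 2 include "Total serum calcium > 9.0 mg/dl or phosphate > 6.0 mg/dL within previous 48h". Section V.A lists among the recorded data "Total serum calcium levels on a daily basis for the first 7 days of the study".

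Neither V.F nor V.G refers to the other. V.G has no provision for held doses and uses neither the peak calcium nor the number of holds.

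**The concern.** The check is meant to show whether the planned regimen reaches its 25D target without an undue rise in calcium. A patient held under V.F is no longer on that regimen, yet the later 25D samples still count as if they were. They pull the mean down for a reason unrelated to whether the planned doses are adequate, so the arm can look under-dosed because someone's calcium rose.

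The calcium condition ought to catch this, but it reads only the change to day 5. A rise that led to a hold and then resolved is largely invisible by then, although daily values are on file.

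The result sets the dose for all remaining calcifediol participants, about 50 - 6 = 44. The protocol names hypercalcemia as the only known toxicity of these agents (section VII.B).

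**Working it through.** V.G gives no operating characteristics, so there is no stated figure to reproduce. The power statement in VI.D does not involve this rule.

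**25D condition**

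Inputs from the protocol: six calcifediol patients; threshold 50 ng/ml; doses of 400 µg on day 0 and 200 µg on days 1 to 4; a fall of about 50% from peak by 24 hours (section I.E). I read the 25D mean as one average over the five days, as the heading of V.G's adjustment table does.

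Assumptions not in the protocol: baseline 20 ng/ml; full-dose mean 52 ng/ml; sampling before the day's dose; and the 50% decline applied to the increment over baseline on every later day.

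Under this model full dosing gives the same increment each day. Call it 1, so the five days sum to 5. The share of the full increment kept under a hold is:

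- from day 1: (1 + 0.5 + 0.25 + 0.125 + 0.0625)/5 = 0.3875
- from day 2: (1 + 1 + 0.5 + 0.25 + 0.125)/5 = 0.575
- from day 3: (1 + 1 + 1 + 0.5 + 0.25)/5 = 0.75
- from day 4: (1 + 1 + 1 + 1 + 0.5)/5 = 0.90

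Held patient's mean H = 20 + 32 × share. Arm mean with k held = [(6 - k) × 52 + k × H]/6.

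| Hold from | H | Arm mean, 1 held | Arm mean, 2 held |
|---|---|---|---|
| day 1 | 32.4 | 48.7 | 45.5 |
| day 2 | 38.4 | 49.7 | 47.5 |
| day 3 | 44.0 | 50.7 | 49.3 |
| day 4 | 48.8 | 51.5 | 50.9 |

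With one patient held, only a hold from day 1 or 2 crosses 50. With two, holds from days 1 to 3 do.

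For baseline b, the largest full-dose mean that can still read as below 50 is b + (50 - b)/[1 - k(1 - share)/6]. Over b = 10 to 25 and hold days 1 to 4, this runs from 50.4 to 54.6 with one held patient and from 50.9 to 60.3 with two. The effect therefore matters when the true mean is near the threshold.

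**Calcium condition**

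Entry calcium is at most 9.0, so a held patient has normally risen by more than 1.0 mg/dl. For the other patients I assume a rise c of 0.1 to 0.2, borrowed from the mean rises with placebo and calcifediol in the daily-dosing trials cited in I.E. The day-5 rise each held patient needs for the mean to reach 0.5 is (6 × 0.5 - (6 - k)c)/k:

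- one held: 3.0 - 5c = 2.0 to 2.5 mg/dl
- two held: (3.0 - 4c)/2 = 1.1 to 1.3 mg/dl

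Two held patients peaking at +1.5, with four others at +0.2, give (3.0 + 0.8)/6 = 0.63 if the rise persists, and escalation is blocked. If half has gone by day 5, they give (1.5 + 0.8)/6 = 0.38, and it is not.

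The direction is the same in both cases: 0.63 and 0.38 both exceed the 0.20 of the other four. The held patients still count against escalation, but less than their peaks would.

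**Interaction with V.F's arm rule**

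One of six patients above 10.7 is 1/6 = 16.7%, which exceeds 10% and calls for a reduction. A patient between 10.0 and 10.7 is held but not counted by that rule. Above 10.7, the same six patients could meet V.F's condition for a reduction and V.G's for an increase.

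**The case against.** A reader might infer that both V.G conditions move towards escalation because of the patient who reacted. The documents do not support that. On the calcium condition a held patient pulls towards escalation only if the day-5 rise has fallen below that of the others; any larger residual rise pulls the other way.

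Nor is the net effect always upward. An illustrative simulation assumed a full-dose mean of 52 and baseline of 20 ng/ml, a 25D SD of 12, other patients' calcium rising by 0.2 (SD 0.4), peak rises of 1.1 to 2.2 in held patients, and holds from day 2 or 3. The chance of escalation was 0.33 with nobody held. With one patient held it was 0.31, 0.44 or 0.46 when all, half or a quarter of the peak rise remained at day 5. With two held it was 0.08, 0.48 or 0.61. The 0.33 shows that chance variation in six patients is itself a large source of wrong escalation.

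Other objections carry weight. With one patient held, crossing 50 in the main illustration needs calcium above 10.0 after one or two doses, whereas I.E reports a mean 24-hour change of only 9.5 to 9.7 mg/dl in healthy volunteers. Slower late elimination would shrink the 25D effect. A rise need not be caused by the drug, since I.V. calcium replacement is expected in some patients (V.A). The mean under the regimen as delivered, holds included, is a legitimate quantity. V.F's individual hold also continues to protect every later participant.

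The DSMB sees unblinded calcium data every 6 months and can alter the trial, and investigators review safety weekly. However, no review is tied to the V.G decision. These points limit the size of the problem. They do not supply the missing rule on how held patients are counted.

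**Conclusion.** The point stands in limited form. V.G followed as written can read a safety hold as under-dosing. In the illustration, one early hold in six moves a full-dose mean of 52 to 48.7 or 49.7, into the escalation row; a single hold from day 3 or later does not. This rests on the assumed baseline, full-dose mean and daily halving, none of which the protocol establishes for this population.

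The day-5 calcium reading is a weakened brake, not a reversed one. How much it weakens depends on how fast calcium falls after a hold, which the documents do not give.

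It would also go too far to say that the plan escalates regardless of toxicity: one of six patients above 10.7 already meets V.F's condition for a reduction. The gap lies mainly between 10.0 and 10.7 mg/dl. Above 10.7 the problem is that V.F and V.G may call for opposite changes with no stated precedence. This is more than a missing detail, because the check sets the dose for about 44 participants, and it should be corrected.

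**What to change.** Reconcile V.F and V.G in the protocol. State how patients held under V.F enter both V.G means, and which rule takes precedence when the two call for different changes.

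For the V.G review, report the 25D mean from samples taken while all scheduled doses had been given, separately from post-hold samples. Beside the day-5 calcium change, show the number of calcifediol patients held and the peak calcium change over days 0 to 5, as a mean and by patient. The thresholds, doses and escalation decision stay with the sponsor and DSMB.

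The cost is protocol wording and a short table, since calcium is already recorded daily and the holds follow from it. The downside is that the on-schedule 25D mean may rest on fewer samples. It should not be read alone, because leaving held patients out also removes their calcium signal. In the simulation above with two patients held, the chance of escalation was 0.35 when they were simply dropped, against 0.04 with full-dose 25D levels and peak calcium. The second figure uses levels that would not be observed after a hold, so it shows the value of keeping the calcium signal and is not a result the trial could reproduce.

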The dosing regimen of calcitriol planned in the current study (4 µg daily for 5 days) represents a dose far lower than dosing regimens that have been used safely in prior studies, and thus is very unlikely to cause hypercalcemia or other adverse events.

G. Rationale behind the proposed research, and potential benefits to patients/society

Despite compelling data from the pre-clinical and epidemiologic studies discussed above, it remains unknown whether administration of vitamin D metabolites (25D or 1,25D) to critically ill patients will have beneficial effects on acute kidney injury (AKI) or other clinically relevant outcomes. Finding an effect of vitamin D metabolites on AKI would represent a major advance in the field, especially since currently there are no drugs or interventions that reliably prevent or treat AKI in humans. Finding a beneficial effect of vitamin D metabolites on AKI in the current study would provide preliminary data to justify a larger interventional study of vitamin D metabolites among critically ill patients, which would be powered to detect hard clinical end points such as need for renal replacement therapy and death. Finally, the current study will answer important questions about vitamin D metabolism in critically ill patients, which will inform future interventional studies of vitamin D metabolites in this and other clinical settings.

II. SPECIFIC AIMS

We will enroll 150 critically ill patients at risk of severe AKI into a 3-arm, double-blind, randomized study of calcifediol (25D), calcitriol (1,25D), or placebo to test the following:

Primary Objective – Prevention of AKI incidence/severity

Test whether administration of calcifediol (25D) or calcitriol (1,25D), compared to placebo, will decrease the incidence/severity of AKI among ICU patients, assessed by daily measurement of SCr over 7 days.

Secondary Objectives – Urinary Injury and Immune/Inflammatory Biomarkers

Test the effects of calcifediol (25D) or calcitriol (1,25D), compared to placebo, on urinary injury biomarkers (NGAL and KIM-1) and key immune/inflammatory markers assessed by monocyte mRNA expression and flow cytometry.

Tertiary Objectives – Clinical Outcomes (exploratory)

Test the effects of calcifediol (25D) or calcitriol (1,25D), compared to placebo, on ICU- and hospital length of stay, mortality, duration of mechanical ventilation, and other clinical outcomes.

III. SUBJECT SELECTION

A. Inclusion and Exclusion Criteria

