Primary end point. The primary end point is a composite of renal injury, RRT, and death. Renal injury will be assessed by time-averaged (area under the curve [AUC]) levels of daily SCr for the first 7 days following enrollment. This end point has been used in previous clinical trials conducted in AKI,⁸⁹ and these measurements will be obtained through routine clinical testing. To account for missing data, we will standardize the AUC of daily SCr levels relative to the number of days in which SCr data are available. RRT and death are important confounders of SCr levels, as well as important end points by themselves, and will therefore be considered along with the AUC of SCr levels as part of the primary composite end point. RRT will be defined as receipt of any form of dialysis within the first 7 days of enrollment. Death will be defined as all-cause mortality within the first 7 days of enrollment.

To evaluate the primary composite end point, which includes both continuous (SCr levels) and dichotomous (RRT and death) variables, we will use a rank-based procedure, as prior studies have done,⁹⁰ as follows:

- Patients who die within 7 days of enrollment will be assigned the highest (worst) rank, with no difference in rank assigned to patients who die at different times within the first 7 days.
- Patients who survive >7 days but who require RRT within 7 days of enrollment will be assigned the second highest rank.
- All other patients will be assigned a rank based on the AUC of their SCr, as described above.

Secondary end points. Secondary end points will include new or worsening AKI (defined by KDIGO guidelines);⁹¹ kidney function on hospital discharge (assessed by SCr); hospital- and ICU length of stay; and hospital-, ICU-, and 28-day mortality. We will also evaluate the AUC of urinary injury biomarkers, including KIM-1, NGAL, and IL-18, during the first 5 days using a similar global rank score strategy as described above. Finally, we will evaluate organ-failure free days (assessed by daily SOFA scores) during the first 7 days following enrollment. For the cardiovascular component of the SOFA score, we will use a modified scoring system that has improved accuracy in predicting outcomes,⁹² and for the renal component we will assign a score of “4” (the highest score) to any participant who requires RRT.

C. Statistical methods

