To evaluate the primary end point, we will compare the ranks between treatment groups versus the placebo group with the use of the Wilcoxon Rank Sum test. To evaluate secondary end points, we will compare means and medians between each of the active treatment groups versus the placebo group using parametric (e.g., t-test) and non-parametric (e.g., Wilcoxon Rank Sum) tests, as appropriate. To account for two active treatment groups, we will consider p values <0.025 to be significant for the primary end point. For secondary end points, all of which will be considered exploratory, we will consider p values <0.05 to be significant.

D. Power analysis

150 participants (N=50 per group) will provide >80% power to detect a 0.62 standard deviation difference in the global rank score in each of the active treatment groups vs. placebo, with a two-sided α of 2.5%.

VII. RISKS AND DISCOMFORTS

A. Complications of surgical and non-surgical procedures

Not applicable

B. Drug side effects and toxicities

The only known toxicity of vitamin D metabolites, including calcifediol and calcitriol, is hypercalcemia.^{81 82} Despite an excellent safety profile, transient hypercalcemia has been reported with calcitriol and, to a much lesser extent, with calcifediol. The risks of hypercalcemia in the current study are low, since the planned doses of calcifediol and calcitriol are lower than doses that have been used safely in prior studies in humans (discussed in detail in sections 1E and 1F). Additionally, the following precautions will further minimize risk to patients:

1) Limiting our study to patients with serum total calcium levels ≤ 9.0 mg/dl. Most prior clinical studies of calcifediol and calcitriol (discussed in sections 1E and 1F) were conducted in patients who were generally normocalcemic on enrollment. In contrast, most ICU patients have serum calcium levels in the low-normal range, and many patients (55.2% in one study)⁹³ are frankly hypocalcemic on arrival to the ICU. In the current study, we will exclude patients with serum total calcium levels > 9.0 mg/dl on enrollment (**Table 2**). By limiting enrollment to patients with serum total calcium levels ≤ 9.0 mg/dl, a substantial barrier exists for serum calcium levels to rise into the hypercalcemic range (>10.7 mg/dl) and an even larger barrier for clinically relevant hypercalcemia (>11.5 mg/dl).

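### The primary Wilcoxon test ranks absolute 7-day serum creatinine and ignores each patient's starting creatinine; adjusting for it is valid, nearly free, and gains power

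*Combined protocol and SAP*

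**What the plan says.** The primary objective (Section II) is that treatment "will decrease the incidence/severity of AKI among ICU patients, assessed by daily measurement of SCr over 7 days".

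Section VI.B defines the renal component of the primary end point: "Renal injury will be assessed by time-averaged (area under the curve [AUC]) levels of daily SCr for the first 7 days following enrollment". It ranks deaths within 7 days worst and RRT within 7 days second worst. For the rest, "All other patients will be assigned a rank based on the AUC of their SCr, as described above". The only standardization is for missing days: "we will standardize the AUC of daily SCr levels relative to the number of days in which SCr data are available".

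Section VI.C then says "we will compare the ranks between treatment groups versus the placebo group with the use of the Wilcoxon Rank Sum test", with p < 0.025 required for each active arm. No covariate or stratum is named. Section VI.D gives more than 80% power with 50 per arm "to detect a 0.62 standard deviation difference in the global rank score in each of the active treatment groups vs. placebo".

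In Section IV.C, "Randomization will be stratified by the presence or absence of AKI on enrollment". That factor is defined by a creatinine rise or low urine output, not by creatinine level, and it does not reappear in the analysis.

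**The concern.** The aim concerns kidney injury, but the ranked quantity is a creatinine level, which mixes injury during the trial with the kidney function the patient brought to it. The entry criteria (Section III.A) make that mixture wide. CKD earns 3 points on the risk score, and only stage V and end-stage disease are excluded. A patient with CKD (3), shock (2) and hypertension (1) reaches the threshold of 6 without any acute kidney injury (AKI).

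Two illustrative patients show the effect:

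- A CKD patient whose creatinine stays at 2.5 mg/dl averages 2.5.
- A patient whose creatinine triples from 0.8 to 2.4 mg/dl averages (0.8 + 2.4)/2 = 1.6 if the rise is linear over 7 days. With a plateau from day 2, the average is (2 × 1.6 + 5 × 2.4)/7 = 2.17.

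Either way, the injured patient gets the better rank.

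Randomization makes this noise rather than bias on average. But noise costs power, and at 50 per arm a chance imbalance in starting creatinine would carry straight into the primary result. That result is meant to inform whether a larger trial is justified.

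**Working it through.** **Inputs from the plan.** 50 per arm; two-sided α = 0.025 per comparison (critical value 2.241); effect 0.62 SD of the global rank score (Sections VI.C and VI.D). The documents give no value for r or for the death and RRT rates, so these are assumed and varied.

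**1. The plan's own figure.** Power = Φ(d√(50/2) − 2.241). With d = 0.62: Φ(3.100 − 2.241) = Φ(0.859) = 80.5%. The stated figure reproduces, though narrowly: a noncentral t calculation gives 79.4%, and allowing for Wilcoxon efficiency of 0.955 gives 78.5%.

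**2. Adjusting for starting creatinine, same effect, no deaths or RRT.** Adjustment multiplies the residual SD by √(1 − r²), so d becomes 0.62/√(1 − r²). The difference detectable with 80% power is (2.241 + 0.842) × √(2/50) × √(1 − r²).

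| r | Power for 0.62 SD | Detectable difference (SD) |
|---|---|---|
| 0 | 80.5% | 0.617 |
| 0.3 | 84.3% | 0.588 |
| 0.5 | 91.0% | 0.534 |
| 0.7 | 98.2% | 0.440 |

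**3. A different reading of the effect.** Suppose 0.62 SD were the effect on injury after removing starting level. The unadjusted test would then see d = 0.62√(1 − r²), with power 76%, 67%, 49% and 35% at r = 0.3, 0.5, 0.7 and 0.8, against about 80% adjusted. This is not how Section VI.D defines the effect, so these figures are not the plan's power.

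**4. Simulation with tied worst ranks.** All inputs here are assumed: 50 per arm; AKI stratum 25/25 in each arm; placebo deaths 9.6% and RRT 6.4% (16% together), with latent correlation to injury of 0, 0.5 or 1; 20,000 trials per setting. Rank-ANCOVA is a regression of the rank on treatment, ranked enrollment creatinine and AKI stratum. Entries are power (%), Wilcoxon → rank-ANCOVA.

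| Effect defined on | Latent correlation | r = 0.3 | r = 0.5 | r = 0.7 |
|---|---|---|---|---|
| Adjusted injury | 0 | 39 → 41 | 33 → 37 | 22 → 29 |
| Adjusted injury | 0.5 | 65 → 67 | 57 → 64 | 43 → 59 |
| Adjusted injury | 1 | 73 → 76 | 65 → 75 | 50 → 71 |
| Full score before ties | 0 | 43 → 45 | 44 → 49 | 43 → 54 |
| Full score before ties | 0.5 | 69 → 72 | 71 → 79 | 76 → 89 |
| Full score before ties | 1 | 77 → 81 | 79 → 87 | 82 → 96 |

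From these rounded entries the gain is 2–4 points at r = 0.3, 4–10 at r = 0.5 and 7–21 at r = 0.7. The absolute levels follow from the assumptions; the differences are what matter. Type I error (60,000 trials per setting, nominal 2.5%) was 2.0–2.4% for Wilcoxon and 2.4–2.6% for rank-ANCOVA.

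**5. A second simulation, without a stratum term, effect set so that Wilcoxon has about 80% power.** Here r is the correlation on the log scale, and treatment does not affect death or RRT.

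| Deaths / RRT | r = 0 | r = 0.5 | r = 0.7 | r = 0.8 | r = 0.9 |
|---|---|---|---|---|---|
| 10% / 5% | 80% | 86% | 91% | 94% | 96% |
| 20% / 10% | 80% | 84% | 86% | 87% | 88% |

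Entries are rank-ANCOVA power. Its type I error stayed at about 2.4–2.7%.

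**6. Chance imbalance (normal approximation, no ties).** Overall the unadjusted test keeps its 2.5%. Given a baseline imbalance of 2 standard errors, its conditional false-positive rate is 7.6% at r = 0.5 and 14.3% at r = 0.8. With an imbalance of only 1 standard error it falls below nominal (2.3% and 0.8%).

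**The case against.** The strongest reply is that nothing is broken. The Wilcoxon test controls type I error and meets the power stated for the effect as the plan defines it. The plan also cites earlier trials for both the creatinine AUC and the rank procedure. On this view, adjustment is a preference. That the test is valid stands; it does not follow that the available precision should be left unused.

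Second, the gain rests on quantities the documents do not supply, and it is small at r = 0.3. This stands too: no single figure can be promised. But the recommendation does not need a particular r, because the cost at r = 0 is negligible. The 98% in step 2 should not be a headline, because it ignores deaths and RRT.

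Third, some of the gain in step 4 might come from the stratum term or from the Wilcoxon test being slightly conservative there. Step 5 has no stratum term and nearly equal test sizes, and the gain persists.

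Fourth, covariate adjustment leaves the two example patients in the same order. That is right: the score remains a level score. What changes is the comparison, which sets each patient's rank against the rank expected for that starting creatinine. The KDIGO and urinary biomarker end points speak more directly to injury, but Section VI.C treats all secondary end points as exploratory.

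**Conclusion.** The concern holds as a loss of efficiency and a weakness of interpretation, not as an invalid analysis. Spread in starting creatinine stays in the primary ranks as noise, and neither it nor the randomization stratum is used in the test.

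The gain from adjustment depends on r and on how many patients fall in the tied worst ranks. Under the assumed 16% deaths and RRT it runs from about 2 points (r = 0.3) to about 21 points (r = 0.7). With Wilcoxon calibrated to 80% power, adjusted power is about 84–96% for r from 0.5 to 0.9. With stated power only just at 80%, the change is worth making.

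**What to change.** Keep the order death, RRT, creatinine AUC. In Section VI.C, make the primary test a rank-based ANCOVA for each active arm against placebo, at two-sided 0.025. Regress the global rank on treatment, with ranked enrollment creatinine as covariate and the AKI randomization stratum as a factor. Report the unadjusted Wilcoxon test as a sensitivity analysis.

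The text should also:

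- define the covariate as one value, for example the last creatinine before the first dose, as distinct from a pre-illness baseline and from the daily values in the AUC;
- add that value to the data list in Section V.A and say how a missing one is handled;
- note in Section VI.D that the stated power refers to the unadjusted score.

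Ranking on AUC relative to enrollment creatinine can be a further sensitivity analysis. It redefines the end point and removes injury already present at entry in patients with stage 1 AKI.

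The cost is wording, settled before unblinding. Pre-randomization creatinine and AKI status are already needed for eligibility and stratification, so no new data, visits or patients are required.
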